**Anterior Bridging Cage With Bone Substitute Versus Localized Autobone in
Transforaminal Lumbar Interbody Arthrodesis**

NCT02485574

2021-07-14

Study protocol

Consecutive patients aged 18-80 years with spinal stenosis or spondylolisthesis who planned to undergo single-level lumbar transforaminal interbody fusion (TLIF) with pedicle screw fixation were included. All operations were performed at a single institution by a single surgeon. The enrolled patients had plain radiographs at postoperative 3, 6, and 12 months and fine-cut multiaxial reconstructed CT scan at postoperative 12 months to evaluate for bone-bridging patterns. The clinical outcomes were assessed by the Oswestry Disability Index (ODI) scores preoperatively and 12 months after surgery.

Operation Methods

After disc preparation following bilateral decompression with facetectomies, extra-cage bone grafting, consisting of half- mixed each 6 cc of local autobone and synthetic bone (OSTEON, Genoss, Korea), was performed on the prepared anterior disc space bilaterally; then, bilateral polyetheretherketone cages (ABB cage, Genoss, Korea) with different graft compositions (left cage: filled with local autobone, right cage: filled with local autobone + synthetic bone) were inserted.

Radiographic Fusion Criterion

We used the concept of InCBB and ExCBB to evaluate the fusion status. InCBB was defined as the bridging bone between the upper and lower vertebrae through the void of the cage(s) and divided into right (Rt.) and left (Lt.) InCBB according to the cage position. ExCBB was defined as the bridging bone between the 2 vertebrae in extra-cage areas of the disc space and divided into 5 zones based on their relative positions to the cages in the disc space: anterior ExCBB: front of the cage; posterior ExCBB: back of the cage; intermediate ExCBB: between 2 cages; right: at the right side of the right cage; and left ExCBB: at the left side of the left cage. We graded bridging scores from 0 to 2 based on the degree of completion of the bridging bone in InCBBs and ExCBBs (grade 0: no bridging at the superior and inferior endplates; grade 1: incomplete bridging; bridging at the superior or inferior endplate, but with a clear radiolucent line; grade 2: complete bridging). We defined ABB as the bridging bone between the extra-cage grafted bone and intra-cage grafted bone through the medial, lateral, superior, and inferior holes in each cage.

InCBB, ExCBB and ABB were evaluated using a software program (Extended Brilliance Workspace 4.5 workstation, V4.5.2.4031, Philips Healthcare Nederland BV, the Nether- lands) that allows users to control the axis of the image planes. Three planes were set at each level as follows: the axial plane was set parallel to the operated disc space on coronal and sagittal views; the sagittal plane was set perpendicular to the disc space on coronal view and the posterior margin of the vertebrae on axial view; and the coronal plane was set perpendicular to the disc space on sagittal view and parallel to the posterior margin of the vertebrae on the axial view. The sagittal and coronal views were then serially examined for ExCBBs and InCBBs. The fusion was defined as meeting the following 3 criteria: no subsidence of 3 mm or more on serial postoperative 3, 6, 12 months radiographs until postoperative 12 months; at least having one or more grade 2 among InCBBs or ExCBBs (InCBB/ExCBB: 0/2, 1/2, 2/2, 2/1, 2/ 0); and the complete bridging bone, graded 2, should be confirmed on both sagittal and coronal views simultaneously. After three planes (sagittal, coronal, and axial) were set at each level, the sagittal and coronal views were serially examined for ExCBBs, InCBBs, and ABBs. To evaluate medial and lateral ABBs, we adjusted the sagittal plane on the axial view in a direction parallel to the diagonal axis of the cage.

Statistical Analysis

The differences between the fused and non-fused groups based on our suggested criterion were examined using independent t-tests for continuous variables. A P value <0.05 was considered statistically significant. All statistical analyses were performed using SPSS version 23.0 (SPSS, Chicago, IL, USA).

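### The title names bone substitute versus autobone; the design can at most compare two in-cage fillings, each fixed to one side, over a shared mixed graft

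*Combined protocol and SAP*

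**What the plan says.** The title sets a cage with bone substitute against local autobone: "Anterior Bridging Cage With Bone Substitute Versus Localized Autobone in" transforaminal lumbar interbody arthrodesis.

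Operation Methods gives the fillings: "left cage: filled with local autobone, right cage: filled with local autobone + synthetic bone". The mixing ratio in the right cage is not stated. Before the cages go in there is "extra-cage bone grafting, consisting of half- mixed each 6 cc of local autobone and synthetic bone (OSTEON, Genoss, Korea"), which "was performed on the prepared anterior disc space bilaterally". The filling is tied to the side in every patient, and no randomisation of side is described.

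Radiographic Fusion Criterion defines in-cage bridging (InCBB), "divided into right (Rt.) and left (Lt.) InCBB according to the cage position", and extra-cage bridging (ExCBB) in five zones, each graded 0 to 2. For the third readout it says: "We defined ABB as the bridging bone between the extra-cage grafted bone and intra-cage grafted bone", assessed through the holes in each cage. The bridging part of the fusion definition requires "at least having one or more grade 2 among InCBBs or ExCBBs". ODI is recorded once per patient before surgery and once at 12 months.

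Statistical Analysis states one test: "The differences between the fused and non-fused groups based on our suggested criterion were examined using independent t-tests for continuous variables". It gives no right-versus-left comparison. The document contains no separate objective, hypothesis or conclusion, so the title is the only statement of the question.

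**The concern.** A reader who takes the question from the title will expect evidence on whether a bone substitute performs like autobone. The arms described do not supply that contrast. The substitute side also contains autobone, and the autobone side also receives synthetic graft outside its cage. The most visible outcomes, fusion and ODI, belong to a level or a patient that contains both fillings.

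At stake is the conclusion. A high fusion rate or a good ODI result could be cited in support of the substitute although neither outcome can separate the two fillings. The statistical section does not guard against this, because its only test splits patients by fusion status and leaves the grafts uncompared.

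**Working it through.** The document gives no sample size, power, effect size or event count on this point, so there is no figure to reproduce. The check sets graft content beside each outcome.

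**1. Graft by location (Operation Methods)**

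| | Left | Right |
|---|---|---|
| Inside cage | autobone; 0% synthetic | autobone plus synthetic; ratio not stated |
| Outside cage | half synthetic | half synthetic |

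Reading the 6 cc as the amount of each component, the extra-cage share is 6 / (6 + 6) = 50% synthetic on both sides. The only cell that differs between sides is the cage filling.

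**2. Which outcomes have a graft comparator**

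- InCBB: one grade per cage, through the cage void. It has a within-patient comparator.
- ABB: assessed per cage, so it also has a comparator. One end of each bridge lies in the shared mixed graft.
- ExCBB: lies outside the cages in the common graft. The anterior, posterior and intermediate zones are not tied to one cage; the right and left zones sit beside differently filled cages but do not read the filling directly.
- Fusion: one value per operated level. A single complete bridge in the shared extra-cage graft can meet the bridging criterion whatever either cage holds.
- ODI: one value per patient per assessment.

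For fusion and ODI the exposure is the same in every patient (autobone left, mixture right). A factor that never varies between patients has no estimable effect on a patient-level outcome. The fused-versus-non-fused test has the same limit, since both groups carry both fillings.

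**3. What a right-minus-left InCBB difference estimates**

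Let D be the right grade minus the left grade in one patient. Then

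mean of D = effect of filling + effect of side.

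If side were allocated at random, the side term would tend to cancel. Here the mixture is always on the right, so the two terms cannot be separated.

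**4. Illustration of how far the sides differ**

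Let E be extra-cage volume per side, V the cage volume and s the synthetic fraction inside the cage. Then

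synthetic share of a side = (0.5E + sV) / (E + V), and right minus left = s(right) × V / (E + V).

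Assumptions not in the document: V from 1 to 3 cc, s(right) = 0.5, and the 12 cc either split equally (E = 6) or used on each side (E = 12).

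- E = 6: left 3/7 = 43% to 3/9 = 33%; right 3.5/7 = 4.5/9 = 50%; difference 7 to 17 points.
- E = 12: left 6/13 = 46% to 6/15 = 40%; right 6.5/13 = 7.5/15 = 50%; difference 4 to 10 points.

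Because the right-cage ratio is not stated, s(right) could be higher. Even at the unattainable limit of 1, the largest difference in this range is 3/9 = 33 points, against 100 for substitute alone versus autobone alone. These figures describe graft content pooled by side. They are not a bias or an effect size, and the conclusion does not depend on them.

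**The case against.** The title can be read loosely: a cage containing some substitute against a cage containing autobone. Operation Methods states the two fillings openly, and the document draws no equivalence conclusion. This stands as far as it goes, so the title is imprecise rather than false. It does not remove the synthetic graft on the autobone side, nor give fusion or ODI a comparator.

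Three stronger readings are tempting, and the document supports none of them.

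- A reader might infer that a null result on ExCBB, fusion or ODI is predetermined. For fusion and ODI no graft comparison exists, so there is no null result to obtain. For ExCBB, the right and left zones adjoin differently filled cages that have lateral holes, so a difference is not ruled out.
- A reader might infer that the shared extra-cage graft spoils the left-right comparison or disqualifies ABB. A background of the same composition on both sides limits how far the result generalises, but does not by itself bias the contrast. Side-specific ABB can still carry some information on the filling.
- A reader might infer that InCBB isolates the filling. It does not: graft is fixed to side, and the cage holes allow in-cage and extra-cage graft to join.

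It is also fair to say that rewording alone repairs neither the fixed side nor the missing paired analysis. The fix therefore covers both: it adds the paired analysis and discloses the confounding, which analysis cannot remove.

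**Conclusion.** The concern holds in a limited form. The contrast named in the title is not made. At most the design compares autobone plus synthetic in the right cage with autobone in the left cage, over the same mixed extra-cage graft, with filling and side inseparable. Fusion and ODI cannot support a graft claim, and the stated test does not address one.

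The consequence is for what may be concluded; no error rate or bias can be calculated from the document. The finding rests on the stated fillings, the bilateral extra-cage graft and both cages being present in every patient, all of which are explicit. It also rests on the absence of any described randomisation of side. The change should be made: it is cheap and determines which results can bear on the graft question.

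**What to change.** - **Title and question.** State the contrast as in-cage autobone plus synthetic (right) versus in-cage autobone (left), with the same mixed extra-cage graft on both sides. Add this as an explicit objective, since there is none.
- **Graft analysis.** Base any graft claim on a within-patient right-versus-left comparison of InCBB grades, for example a Wilcoxon signed-rank or sign test on the 0 to 2 grades, or McNemar's test on grade 2 versus lower. If results have already been seen, label this as added afterwards.
- **Secondary.** Report side-specific ABB as a paired readout, noting the shared extra-cage graft at one end.
- **Descriptive only.** Report ExCBB, fusion and ODI without a graft claim.
- **Limitation.** State that graft is confounded with side, because each filling is fixed to left or right and no randomisation of side is described.

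The cost is wording plus one paired analysis of grades the protocol already collects. Surgery and graft composition are unchanged. The downside is a narrower claim, still qualified by side.

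### The fused versus non-fused comparison is unadjusted, so a 12-month ODI difference could partly reflect age and indication if it is read as clinical support for the fusion criterion

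*Combined protocol and SAP*

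**What the plan says.** **Entry (Study protocol section).** The plan takes "Consecutive patients aged 18-80 years with spinal stenosis or spondylolisthesis". The surgery must be a planned TLIF at one level, fixed with pedicle screws. It adds that "All operations were performed at a single institution by a single surgeon". No exclusion criteria are given, and no rule says how to class a patient who has both diagnoses.

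**Outcome (same section).** "The clinical outcomes were assessed by the Oswestry Disability Index (ODI) scores preoperatively and 12 months after surgery". No other clinical outcome is named.

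**Groups (Radiographic Fusion Criterion section).** "The fusion was defined as meeting the following 3 criteria": subsidence staying under 3 mm on the radiographs through month 12, at least one grade 2 bridge inside or outside the cages, and that bridge visible in both the sagittal and coronal planes.

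**Analysis (Statistical Analysis section).** "The differences between the fused and non-fused groups based on our suggested criterion were examined using independent t-tests for continuous variables". The significance level is set at 0.05. The continuous variables are not listed. No covariate, stratum or regression model is stated, and no test for a categorical variable such as indication.

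**The concern.** Fused and non-fused are not allocated groups. A patient enters one or the other because of what the images show up to a year after surgery. Age spans 80 − 18 = 62 years and two indications are pooled. Either factor could plausibly bear both on bridging or subsidence and on disability at 12 months. If so, the two groups would differ in mean ODI even if fusion itself made no difference to disability.

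This matters because the groups rest on a criterion that the plan describes as its own suggestion. An ODI difference in favour of fused patients would be a natural argument that the criterion is clinically meaningful. With an unadjusted comparison, a reader cannot tell how much of that difference belongs to the criterion and how much to who is older or has which diagnosis.

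**Working it through.** **Plan's own figure.** There is none to reproduce: the documents state no sample size, power, SD, fusion rate or expected difference. Everything below rests on assumed inputs and serves only to bracket the size.

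**Step 1: spurious difference.** With no true fusion effect, the expected unadjusted difference is the covariate's effect on ODI times its imbalance between groups.

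- Age: groups 5 years apart, 0.3 ODI points per year: 5 × 0.3 = 1.5 points. Over 3 to 10 years and 1 to 3 points per decade, the range is 3 × 0.1 = 0.3 to 10 × 0.3 = 3.0 points.
- Indication: shares 30 percentage points apart, 5 ODI points between indications: 0.30 × 5 = 1.5 points.
- Same direction: 1.5 + 1.5 = 3 points. Opposite directions: 1.5 − 1.5 = 0. Even the sign of the combined effect is not known in advance.

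**Step 2: rejection rate of the t-test.** SE = SD × √(1/n₁ + 1/n₀). For a spurious difference d, the two-sided 5% rejection rate (normal approximation) is Φ(d/SE − 1.96) + Φ(−d/SE − 1.96). The plan does not state sidedness; two-sided is assumed.

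| Fused / non-fused | SD | SE | d = 0 | d = 1.5 | d = 3 | d = 5 |
|---|---|---|---|---|---|---|
| 90 / 10 | 14 | 4.67 | 0.050 | 0.062 | 0.099 | 0.188 |
| 90 / 10 | 18 | 6.00 | 0.050 | 0.057 | 0.079 | 0.133 |
| 80 / 20 | 14 | 3.50 | 0.050 | 0.071 | 0.137 | 0.298 |
| 80 / 20 | 18 | 4.50 | 0.050 | 0.063 | 0.102 | 0.199 |

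**Step 3: check by simulation.** Indication only, 20,000 replicates per cell, 80% fused, ODI SD 15 within indication, no true fusion effect. The two figures in each cell are for a 5-point and a 10-point ODI gap between indications.

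| Share with a given indication, fused vs non-fused | Spurious difference | N = 60 | N = 100 | N = 200 |
|---|---|---|---|---|
| 50% vs 50% | 0 | 0.050, 0.053 | 0.052, 0.051 | 0.051, 0.050 |
| 60% vs 40% | 1, 2 points | 0.055, 0.069 | 0.059, 0.079 | 0.064, 0.114 |
| 70% vs 30% | 2, 4 points | 0.067, 0.123 | 0.078, 0.172 | 0.111, 0.300 |

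Both routes show the same pattern: about 5% with no imbalance, 5.5-6% when it is slight, and up to about 30% when imbalance, covariate effect and sample size are all at the upper end.

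**The case against.** The strongest answer is that the plan makes no causal claim. It says that differences between the groups were examined. For that null, equal group means, confounding does not inflate the error of the t-test: a difference due to age is still a real difference in means. This stands, and it confines the rejection rates above to one reading of the result.

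Several stronger readings are tempting, and the documents do not support them:

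- *Entry is unrestricted, or too broad.* It is limited to planned single-level TLIF with pedicle screws, by one surgeon at one institution. What is absent is a list of exclusions. Broad consecutive enrolment is not a defect.
- *The groups are self-selected.* They are classified by imaging criteria; patients choose nothing.
- *The analysis ignores both entry variables.* This is supported for indication, which is categorical and has no stated test. Age is continuous and may be among the unlisted variables tested. A separate test of age would show an imbalance but would not adjust ODI for it.
- *Patient mix undermines the titled graft comparison.* Under Operation Methods every patient receives both graft compositions, one in each cage, so age and indication are the same on both sides of a left versus right contrast. That no such contrast is specified is a separate matter.

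It is also fair that no figure in the documents links age or indication to fusion or ODI, and that ODI is not named as a tested variable. As the only clinical outcome, and a continuous one, it is the obvious candidate.

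**Conclusion.** The point holds in a limited form. The one stated comparison is between groups defined by a post-surgical outcome, with neither balance nor adjustment for age or indication, so a 12-month ODI difference cannot by itself be credited to meeting the fusion criterion. The size cannot be fixed from the documents: on assumed SDs of 14 to 18, 10 to 40 non-fused patients and spurious differences of 1 to 5 points, the rejection rate with no true fusion effect runs from about 5-6% to about 30%.

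A reader might infer that the stated 5% level is invalid or that the plan asserts an effect of fusion. Neither follows. The level is correct for equal means, and the causal reading is a foreseeable use of the result, not something the plan states. Severity is low, because the titled graft question is not touched.

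**What to change.** Keep the entry rule. In the Statistical Analysis section:

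1. Estimate the fused versus non-fused difference in 12-month ODI, with a 95% confidence interval, from a linear model with age, indication and preoperative ODI as covariates. Report the unadjusted t-test beside it.
2. Take indication as recorded at entry, and class patients who have both diagnoses by one fixed rule written down before the analysis.
3. Tabulate age and indication by fusion status.
4. Label the comparison as an association, since adjustment for three covariates does not make it an effect of fusion.

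**Cost.** Some wording and one regression. Age and indication are entry criteria, and preoperative ODI is already collected. With indication in two classes, the model uses three more degrees of freedom than the t-test (for example 60 − 5 = 55 instead of 60 − 2 = 58). The real limit is the number of non-fused patients: with 10 of 100 the unadjusted 95% half-width is already 1.96 × 4.67 ≈ 9.1 to 1.96 × 6.00 ≈ 11.8 ODI points, and an adjusted estimate may also be imprecise. If the model is not stable, the table and the label are still worth having and cost almost nothing.

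### Cage filling is tied to side in every patient, so a right-left contrast mixes filling with side, and the planned t-tests compare no grafts

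*Combined protocol and SAP*

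**What the plan says.** - **Title:** "Anterior Bridging Cage With Bone Substitute Versus Localized Autobone". This is the only text that poses a graft comparison.
- **Study protocol:** patients were enrolled consecutively and operated on by one surgeon at one institution. The purpose given for the CT is broader than the title: "fine-cut multiaxial reconstructed CT scan at postoperative 12 months to evaluate for bone-bridging patterns".
- **Operation Methods:** the approach is bilateral ("After disc preparation following bilateral decompression with facetectomies"), and the extra-cage graft is a single autobone and synthetic mixture placed on both sides. The cages were then placed "with different graft compositions (left cage: filled with local autobone, right cage: filled with local autobone + synthetic bone) were inserted".
- **Radiographic Fusion Criterion:** in-cage bridging (InCBB) is "divided into right (Rt.) and left (Lt.) InCBB according to the cage position". The lateral extra-cage zones (ExCBB) are also recorded by side: "right: at the right side of the right cage; and left ExCBB: at the left side of the left cage". Fusion is defined once for the operated level; on the bridging criterion it requires "at least having one or more grade 2 among InCBBs or ExCBBs".
- **Statistical Analysis:** "The differences between the fused and non-fused groups based on our suggested criterion were examined using independent t-tests for continuous variables", at P < 0.05. No right-left, paired or graft comparison is described.

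The documents give no sample size, expected bridging rate or expected effect.

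**The concern.** Two things follow from the fixed rule.

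First, the described analysis does not address the title question. The t-tests group patients by outcome, and every patient in both groups received both fillings. The side rule does not bias these tests; they simply carry no information on one graft against the other.

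Second, the design offers one contrast between the two cage fillings: right against left, in InCBB or in bridging through the cage holes (ABB) by cage. In that contrast filling and side are the same variable. Pairing within the patient removes differences between patients, but not differences between sides. With a single surgeon, a consistent side habit would not average out over operators either.

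At stake is whether a right-left difference, or the absence of one, could be reported as a finding about graft. It could not, because a side effect could create, mask or reverse a filling effect.

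**Working it through.** There is no figure in the plan to reproduce. The main result is algebra; the percentages after it are illustrations.

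**1. What a right-left contrast estimates.** Let g be the effect of filling (mixed minus autobone) and s the effect of side (right minus left), taken as additive. The mixed filling is always on the right, so

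E(R − L) = g + s

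for every patient. The sample size does not enter, so more patients only estimate g + s more precisely.

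**2. What randomising side would give.** With mixed filling on the right, the mean of R − L is s + g. With mixed filling on the left, it is s − g. Half the difference between the two sequences is

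[(s + g) − (s − g)] / 2 = g.

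The side effect cancels. This does not raise power when s = 0; its benefit is that the filling estimate no longer depends on s.

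**3. Illustration: how often a pure side effect would look like a graft effect.** All inputs are assumed: mean grade 2 rate 70% per cage, bivariate normal latent correlation 0.5 between sides, g = 0, two-sided 0.05. The discordant proportion is then 0.286, 0.289 and 0.296 at side differences of 0, 5 and 10 points. At 10 points, for example, the two discordant cells are (0.296 + 0.10)/2 = 0.198 and (0.296 − 0.10)/2 = 0.098. Rejection probabilities by exact enumeration:

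| Test | N | s = 0 | s = 5 points | s = 10 points |
|---|---|---|---|---|
| Exact McNemar | 50 | 2.7% | 6.1% | 18.0% |
| Exact McNemar | 100 | 3.0% | 10.8% | 37.7% |
| Exact McNemar | 500 | 4.1% | 51.8% | 98.4% |
| Paired t-test | 50 | 4.6% | 9.4% | 24.6% |
| Paired t-test | 100 | 5.2% | 15.7% | 46.5% |

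The N = 500 row is there only to show that a larger trial makes the problem worse.

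**4. Sensitivity.** For McNemar, over mean rates of 50, 70 and 85% and correlations of 0, 0.5 and 0.7:

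- 5 points: 5.0–6.9% at N = 50 and 8.5–18.0% at N = 100.
- 10 points: 11.8–28.5% at N = 50 and 24.8–65.4% at N = 100.

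A separate calculation with a left rate of 60%, a right rate of 50% and independent sides gives 11.9% and 25.0%. With side randomised per patient under those inputs, the rate stays at 3.0% and 3.7%.

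**5. Could the extra-cage zones serve as a check on side?** The graft outside the cages is the same mixture on both sides, so a right-left difference in ExCBB would hint at a side effect. If ExCBB behaved like InCBB under the assumptions above, the half-width of its 95% CI would be 1.96 × √(0.286/N). That is 14.8 points at N = 50 and 10.5 at N = 100 (ranges 10.5–19.6 and 7.4–13.9 over the same settings). A null result would not exclude side effects of that size.

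**The case against.** The strongest reply is that the confounding touches nothing in the plan. No right-left test is described, the t-tests are unaffected by the side rule, and harm needs three things the documents do not show: such a test, a causal reading of it and a real side effect. The surgery is bilateral with the same extra-cage graft on both sides, and the within-patient design already removes patient-level confounding. Read by its body, this is a study of bridging patterns and of a fusion criterion; only the title asks about graft. The percentages rest on assumed inputs and range widely. The text is in the past tense, so randomising side is probably no longer possible. A further point is that autobone in the left cage can be set against the mixed graft outside the cages, so right against left is not the only composition contrast.

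Most of this stands as a limit on weight. The side effect may well be near zero, in which case the practical harm is near nil, and the percentages show scale only. But the design cannot show that s is zero. The left-cage against extra-cage contrast is confounded with location and does not compare the two cage fillings. The absence of a right-left test also leaves the title question either unanswered or answered by a contrast that cannot separate filling from side. Either outcome needs a statement in the report.

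**Conclusion.** The concern holds and should be fixed. Two conclusions rest on the text alone: the described t-tests contain no graft contrast, and filling and side coincide in every patient. That a right-left contrast estimates g + s at any sample size follows from this, given additive effects. The size and direction of s are unknown, so no bias in a planned result is demonstrated. Confidence is high on the structure; the practical importance depends on a side effect that the documents neither show nor rule out.

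**What to change.** **Patients already treated under the fixed rule (probably all of them).**

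- State that the fused versus non-fused t-tests do not compare grafts.
- Report any in-cage comparison as a paired contrast of the right mixed-graft cage with the left autobone cage, with its 95% CI. Label it as filling plus side and make no causal claim about graft.
- Optionally, add the paired right-left ExCBB difference with its 95% CI as a weak check on side. State its limits: it assumes side acts alike inside and outside the cage, the in-cage filling may influence the outer zones through the cage holes, and a null result settles little.

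**Any patients still to be operated on.** Randomise, per patient, which side receives which of the two fillings already in use. Compare the R − L differences between the two allocation sequences, so that the side term is removed.

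**Cost.** For treated patients: two sentences of wording and a conclusion that gives up the causal graft claim; the optional check is one table from grades already recorded. For new patients: a randomisation list and one protocol sentence. Neither needs extra patients, scans or readings.

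### Does the 3 mm subsidence criterion for fusion miss settling before month 3, because it names no reference image or measurement method?

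*Combined protocol and SAP*

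**What the plan says.** The section Radiographic Fusion Criterion introduces the composite with "The fusion was defined as meeting the following 3 criteria". The first condition is "no subsidence of 3 mm or more on serial postoperative 3, 6, 12 months radiographs until postoperative 12 months". The second asks for a complete bridge in at least one zone inside or outside the cages. The third is that "the complete bridging bone, graded 2, should be confirmed on both sagittal and coronal views simultaneously".

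The imaging schedule is in the opening section, Study protocol: "The enrolled patients had plain radiographs at postoperative 3, 6, and 12 months and fine-cut multiaxial reconstructed CT scan at postoperative 12 months". That section gives the Oswestry index an explicit baseline, with "scores preoperatively and 12 months after surgery". For the bone-bridging readings, "InCBB, ExCBB and ABB were evaluated using a software program", and the text goes on to say how the three image planes are set. It says nothing comparable for subsidence.

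The classification feeds the one comparison described under Statistical Analysis: "The differences between the fused and non-fused groups based on our suggested criterion were examined using independent t-tests for continuous variables".

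**The concern.** A limit in millimetres needs a starting image and a way to measure, and criterion 1 has neither. The omission stands out because the document is careful elsewhere: it names the workstation software, sets the planes and grades the bridges from 0 to 2.

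The earliest postoperative image listed is the 3-month film. If subsidence is the change between listed films, only settling after month 3 can be seen. A cage that sank early and then stabilised would pass, and the patient would count as fused if a complete bridge was also confirmed on both views. The fused and non-fused groups are the only ones compared, so a criterion that is too lenient could move patients between them. Two readers using different references could also classify the same patient differently.

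**Working it through.** **Inputs.** The 3 mm limit and the three film times come from Radiographic Fusion Criterion, and the imaging list from Study protocol. The documents give no figure for subsidence, so there is none to reproduce.

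**Step 1: when the choice of reference matters.** Let E be settling from surgery to month 3, L settling from month 3 to month 12, and T = E + L.

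- Reference at month 3: pass if L < 3 mm.
- Reference at or soon after surgery: pass if T < 3 mm.

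The readings disagree, with a pass on the first and a fail on the second, when L < 3 and T ≥ 3. Since L = T − E, this means E > T − 3.

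| Total T | Early part E must exceed | As a share of T, (T − 3)/T |
|---|---|---|
| 3 mm | 0 mm | 0% |
| 4 mm | 1 mm | 25% |
| 5 mm | 2 mm | 40% |
| 6 mm | 3 mm | 50% |

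So the choice of reference could matter. The table does not show which reference applies.

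**Step 2: whether the text sets the reference at month 3.**

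- Criterion 1 lists the 3-month film with the 6- and 12-month films as one on which subsidence is judged. If it were the reference, subsidence at month 3 would be zero by definition and listing it as an assessment time would be pointless.
- The closing words of the criterion fix an end at month 12 and no start. Cumulative settling since surgery fits them at least as well as change from month 3.
- The imaging sentence lists follow-up images for assessing bone bridging. It mentions no preoperative imaging either, although patients entered with stenosis or spondylolisthesis and a planned single-level fusion. The absence of an early postoperative film from that list is weak evidence that none existed.
- Subsidence can be read on a single film, as cage penetration past the endplate. That needs no earlier film and includes settling before month 3.

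The month-3 reference is therefore one possible reading, and not the most natural one.

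**Step 3: direction.** On the month-3 reading, the rule can only add patients to the fused group if measured settling is never negative. With film error it can be. For illustration, measured E = −0.5 mm and L = 3.2 mm give T = 2.7 mm, which fails on the month-3 reference and passes on the early one.

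**Step 4: size.** The share of patients whose fusion class would change in the lenient direction is s × c × b, where

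- s is the share with T ≥ 3 mm,
- c is the share of those with L < 3 mm,
- b is the share of those with a confirmed complete bridge.

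The documents give none of the three. Any percentage would only restate assumed inputs.

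**The case for a change.** The strongest case for acting is that the gap is real and needs no assumption to see. Neither reference nor method is written down, the other components of fusion are specified closely, and all three conditions must hold for a patient to be called fused. If an earlier film was used, one sentence would have said so.

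The description is incomplete, and that part stands. It does not follow that the rule is wrong. To say that early settlers are misclassified, one must assume both that month 3 was the reference and that total settling since surgery is the right quantity. The document states neither. If the aim was to detect progressive settling on follow-up films, nobody is misclassified even on the month-3 reading.

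Re-measuring would bring its own difficulty. Film change for patients with an early film and CT penetration for the rest would put two measures that are not interchangeable into one classification, with no rule for combining the two cages. It would also be post hoc, since the text is written in the past tense and data collection appears complete.

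**Conclusion.** No change to the plan follows. Criterion 1 leaves its reference image and measurement method unwritten, a detail that a radiographic reader would fill sensibly and that a report of the results would normally name. The reading that would make the rule defective is not stated and sits poorly with the list of assessment films.

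The reach is also limited. A patient who passes criterion 1 still needs a complete bridge confirmed on two views to be called fused. The bridging grades in the left and right cages, where the graft compositions differ, do not depend on subsidence. The number of patients affected and the direction of any bias in the t-tests cannot be determined from the documents.

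This conclusion rests on one assumption: that a single sensible method was applied to all patients. Evidence that month 3 was in fact the baseline would call for describing the criterion as covering only later subsidence. The documents contain no such evidence.
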